1 PROTOCOL SUMMARY

1.1 SYNOPSIS			
Title:	RANDOMIZED DOUBLE-BLIND PLACEBO-CONTROLLED PROOF-OF-CONCEPT TRIAL OF RESVERATROL FOR THE OUTPATIENT TREATMENT OF MILD CORONAVIRUS DISEASE (COVID-19)		
Study Description:	•	trial to determine the safety and explore the efficacy of using itamin D3 to treat patients with mild COVID-19	
Objectives:	Primary Objective:	To compare the 21-day hospitalization rate among early or mild stage COVID-19 patients taking a 15-day regimen of resveratrol pus vitamin D3 to that for patients taking an identical placebo regimen.	
	Secondary Objectives:	Decrease morbidity and mortality in terms of reduced days of symptoms, reduced rate of ICU admission, reduced rate of mechanical ventilation, and reduced mortality.	
Endpoints:	Primary Endpoint:	Hospitalization rate	
	Secondary Endpoints:	ICU Admission rate, invasive ventilation rates, duration of symptoms, and mortality rates.	
Study Population:	200 hundred patients (100 per group) 45 years and older who test positive for SARS- COV2 who have mild COVID-19 based on WHO Baseline Severity Categorization		
Phase:	2		
Description of Sites/Facilities Enrolling Participants:	Outpatients presenting to COVID-19 testing sites of Mt Carmel Health Systems in Columbus, OH, which may include drive-thru testing centers, emergency departments, urgent care centers.		
Description of Study Intervention:	Patients will be placed on a 15-day course of two 500 mg resveratrol capsules 4 times per day, versus the same dosing frequency of placebo. Both groups will receive 100,000 IU on day one only.		
Study Duration	: up to 6 months		
Participant Duration:	60 days		

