9.2 SAMPLE SIZE DETERMINATION

[figure not shown]
The maximum total number of randomized subjects is capped at 200 by FDA request. We present power analyses of the primary outcome measure (hospitalization) assuming multiple placebo arm

hospitalization rates and effect sizes, as well as for secondary outcome measures. No interim analyses for efficacy are planned, and none are included in the following power calculations.

The primary outcome measure is hospitalization within 21 days of randomization. We provide conservative power estimates by assuming a binary outcome with 5% non-informative loss to follow-up before 21 days. We anticipate this relatively low rate of loss because the endpoint is designed to be evaluable by chart review unless the subject withdraws consent. Hypotheses are as specified in the previous section, and the Z statistic for a two-proportion test is used. The primary Kaplan-Meier analysis will yield slightly better power by treating the outcomes of patients lost to follow-up as censored at the time of last follow-up.

The rate of hospitalization among confirmed cases of COVID-19 ranges between 21% in the 45-54 age bracket, up to 31% for patient's >85 (CDC, 2020). We assumed a mid-point hospitalization rate of 25% for the initial sample size calculation. To achieve 80% power at the 5% two-sided significance level with complete follow-up on 95 subjects per arm with two-sample proportion test, we require a 10% or lower hospitalization rate in the resveratrol arm, compared to a 25% rate in the placebo arm (estimated by power.prop.test, R statistical software). This corresponds to an odds ratio of 1 / 3.

The required resveratrol arm event rate for various placebo arm event rates are plotted in Figure 3. This curve applies to the power for all outcome measures, with lower rates of all secondary outcome events expected to be lower in both arms.

95 complete observations per arm, 80% power

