9.4 STATISTICAL ANALYSES

9.4.1 GENERAL APPROACH

Uncensored data will be summarized by percentages, means and standard deviations, or medians and ranges as appropriate for each variable's distribution. Data subject to censoring (e.g., hospitalization) will be summarized by Kaplan-Meier estimate.

Unless otherwise noted, all hypothesis tests will be two-sided and at the 5% significance level. Similarly, confidence intervals will be two-sided and at the 95% confidence level. Declarations of superiority will be declared if the corresponding hypothesis test is significant and the direction of the estimated treatment effect is favorable to resveratrol.

In addition to local hypothesis tests, we will use a multiple testing procedure to control the familywise Type I error at 5% for the primary and secondary endpoints together. The primary efficacy endpoint (hospitalization) will be tested at the 5% significance level; then, if the primary endpoint null hypothesis is rejected, the two secondary endpoints (ICU admission, invasive ventilation) will be tested via the Bonferroni-Holm procedure. No multiple testing adjustment will be made for exploratory or safety analyses.

Hospitalization, ICU admission, and invasive ventilation endpoints are composites that include death within 21 days of randomization.

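### Section 9.2 extends its 80%-power curve to every outcome, but the curve fits only unadjusted 5% tests and not the gated Holm tests of the secondary endpoints in 9.4.1

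*Combined protocol and SAP*

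**What the plan says.** Section 9.2 introduces its calculations as covering the primary and the secondary outcome measures. The stated design point is: "To achieve 80% power at the 5% two-sided significance level with complete follow-up on 95 subjects per arm", the plan requires a "10% or lower hospitalization rate in the resveratrol arm, compared to a 25% rate in the placebo arm". The method is R's power.prop.test, described as "the Z statistic for a two-proportion test is used". The 95 per arm comes from 100 randomized, "assuming a binary outcome with 5% non-informative loss to follow-up before 21 days". Figure 3 then plots the resveratrol rate needed at each placebo rate and is labelled "95 complete observations per arm, 80% power". Of this curve the section says: "This curve applies to the power for all outcome measures". The same sentence expects secondary event rates to be lower in both arms. No secondary rate is given.

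Section 9.4.1 sets the decision rule. The primary is tested at 5%; "then, if the primary endpoint null hypothesis is rejected, the two secondary endpoints (ICU admission, invasive ventilation) will be tested via the Bonferroni-Holm procedure". It keeps local hypothesis tests alongside this procedure, two-sided at 5% by default.

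The secondary denominator is described in two ways. Section 9.1 frames the secondary hypotheses among patients hospitalized within 21 days. Section 9.4.3 analyses the intention-to-treat population.

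**The concern.** The curve assumes one test at 5% with no precondition. A familywise-controlled secondary claim faces two further hurdles. The primary must be significant, and the smaller of the two secondary p-values must then be below 2.5%. A curve for the easier test overstates power for the harder one, and 9.2 gives no figure at the Holm level or through the gate.

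The low-rate end matters as well. If secondary events are rare, the formula may allow no effect large enough for 80% power, so pointing the reader to the curve gives no usable answer.

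At stake is how a null ICU or ventilation result is read. Someone relying on 9.2 would judge it against a curve labelled 80% when the controlled test has less power.

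**Working it through.** The plotted figure was not available, so the curve is rebuilt from the inputs stated in 9.2: n = 95 per arm, two-sided alpha 5%, power 80%, pooled two-proportion Z.

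**Formula** (as in power.prop.test). With d = p1 − p2, p̄ = (p1 + p2)/2, A = √[2p̄(1 − p̄)] and B = √[p1(1 − p1) + p2(1 − p2)]:

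power = Φ[(d√n − z·A)/B], with z = 1.960 at 5% and 2.241 at 2.5%.

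**1. The plan's own figure.** At 25% v 10% the formula gives 78.1% at 5%. The exact 80% solution is 9.7%, which rounds to the stated 10%. The stated figure reproduces.

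**2. The same points at Holm's first step.**

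| Placebo | Resveratrol for 80% at 5% | Power at 2.5% |
|---|---|---|
| 10% | 0.85% | 71.0% |
| 12% | 1.77% | 71.0% |
| 15% | 3.34% | 71.0% |
| 25% | 9.70% | 71.0% |

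The value is constant because A/B = 1.021 at every point on the curve. The z-score falls from 0.842 by (2.241 − 1.960) × 1.021 = 0.287 to 0.554, and Φ(0.554) = 71.0%. At the rounded 25% v 10% point the figure is 68.8%.

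**3. Adding the gate, by formula.** Take 80% for the primary and 71.0% for the secondary at 2.5%, joined by a bivariate normal. If independent, 0.80 × 0.710 = 57%. At correlations of 0.75, 0.90 and 0.95 the result is 66%, 69% and 70%. The documents give no correlation.

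**4. Adding the gate and full Holm, by simulation.** There were 400,000 trials per scenario, with hospitalization 25% v 9.70%, ICU nested in hospitalization, ventilation nested in ICU, and pooled Z tests.
- ICU on the curve at placebo 10%, 12% or 15%, ventilation at half the ICU rates: gated Holm power for ICU is 67–68%.
- Both secondaries on the curve (ICU/ventilation placebo rates 15%/12% or 12%/10%): 70%. A 15%/10% pairing gives 71%, so the upper end is approximate.

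Simulated values should not be subtracted from the formula's 71.0%. On the simulation scale, ungated ICU power at these points is 84–86% at 5% and 74–78% at 2.5%. The like-for-like fall is from 84–86% to about 67–70%.

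**5. Where the curve ends.** Set the resveratrol rate to 0% and solve for 80% power.
- 5% level: p1 = 7.84%. Here d√n = 0.764, A = 0.2745, B = 0.2688, and (0.764 − 1.960 × 0.2745)/0.2688 = 0.84.
- 2.5% level: p1 = 9.41%. Here d√n = 0.917, A = 0.2994, B = 0.2919, and (0.917 − 2.241 × 0.2994)/0.2919 = 0.84.

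These are normal-approximation limits. With exact binomial probabilities they are 5.7% and 7.0%.

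**6. Denominator.** All of this uses 95 per arm, as in 9.4.3. Under the wording of 9.1 the denominators would be about 95 × 0.25 = 24 and 95 × 0.10 = 10, and the curve would not apply.

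**The case against.** The best defence is that Figure 3 is a generic detectability curve for a binary outcome. It shows the effect needed at each placebo rate and is correct for the local 5% tests that 9.4.1 keeps. That stands: the sentence is incomplete, not wrong for every secondary test. It is also true that 2.5% is only the first Holm step. Once one secondary is rejected the other is tested at 5%, so 71.0% is a floor for each endpoint before the gate is counted. With the sample capped at 200, no decision rule depends on the sentence. None of this makes the curve fit the controlled tests, and 9.2 offers no other power statement for them.

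Three stronger readings are tempting but unsupported.
- A reader might infer that the plan promises 80% power for ICU admission and ventilation at their expected rates. It gives no such rates and says only that they will be lower.
- A reader might blame the gate or Holm for 80% being out of reach at low rates. The limit already exists at 5%, near 7.8%; Holm only moves it to 9.4%.
- A reader might put secondary power at 11–25%. Figures of that size arise if 20–40% of hospitalized patients are assumed to reach ICU in both arms at 25% v 10% hospitalization. Those fractions are not in the documents and the points lie off the curve. The ungated 5% test there already has only about 18–37% power, so low event rates explain most of the shortfall.

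**Conclusion.** The concern holds in a limited form. The curve in 9.2 fits the primary endpoint and the unadjusted local 5% tests, provided 95 patients per arm is the denominator. It does not give the power of the secondary tests under 9.4.1. For points on the curve that power is 71.0% at the 2.5% step, which needs no assumption beyond the plan's formula, and it falls further through the gate. The simulated 67–70% rests on nested endpoints, hospitalization at 25% v 9.7% and assumed ventilation rates. It should not be quoted without them, since weaker correlation brings it down towards 57% on the formula scale. The calculation takes the gate as one 5% Z test and leaves out the alpha spending in 9.4.6 and the covariate-adjusted model in 9.4.2.

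The low-rate limit is a separate weakness of the same sentence. Whether the secondaries fall below it cannot be settled from the documents. This warrants a correction of wording and does not threaten the primary analysis.

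**What to change.** Replace the sentence in 9.2 with:

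> Figure 3 uses an unadjusted two-sided 5% test and applies to the primary endpoint and to local, unadjusted tests of secondary endpoints analysed in all randomized patients. Under the gated Holm procedure of 9.4.1, power for the secondary endpoints is lower: about 71% at the 2.5% step for points on this curve, and lower again once the primary gate is counted. At placebo event rates below about 8% (5% level) or 9% (2.5% level), this formula gives no effect with 80% power.

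Also reconcile 9.1 (secondary hypotheses among hospitalized patients) with 9.4.3 (intention-to-treat), because 95 per arm applies only under the latter. A second curve at two-sided 2.5% would be a useful option.

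The cost is protocol and SAP wording and a less favourable statement of secondary power. The power correction needs no extra patients and changes no test.

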9.3 POPULATIONS FOR ANALYSES

- Intention-to-treat (ITT) population: all randomized participants.
- Safety population: all randomized participants who report taking at least one dose of their assigned medication.

9.4 STATISTICAL ANALYSES

9.4.1 GENERAL APPROACH

Uncensored data will be summarized by percentages, means and standard deviations, or medians and ranges as appropriate for each variable's distribution. Data subject to censoring (e.g., hospitalization) will be summarized by Kaplan-Meier estimate.

Unless otherwise noted, all hypothesis tests will be two-sided and at the 5% significance level. Similarly, confidence intervals will be two-sided and at the 95% confidence level. Declarations of superiority will be declared if the corresponding hypothesis test is significant and the direction of the estimated treatment effect is favorable to resveratrol.

In addition to local hypothesis tests, we will use a multiple testing procedure to control the familywise Type I error at 5% for the primary and secondary endpoints together. The primary efficacy endpoint (hospitalization) will be tested at the 5% significance level; then, if the primary endpoint null hypothesis is rejected, the two secondary endpoints (ICU admission, invasive ventilation) will be tested via the Bonferroni-Holm procedure. No multiple testing adjustment will be made for exploratory or safety analyses.

Hospitalization, ICU admission, and invasive ventilation endpoints are composites that include death within 21 days of randomization.

9.4.2 ANALYSIS OF THE PRIMARY EFFICACY ENDPOINT(S)

The primary efficacy endpoint is hospitalization for any cause within 21 days after randomization, as established by medical record review. Outcomes of subjects who withdraw consent or are otherwise lost to follow-up before 21 days will be considered missing. The intention to treat population for the hospitalization endpoint will be used for analysis. A logistic regression model will be fit with age, sex, race, ethnicity, risk group (see Sec 9.4.7), and randomized group as covariates, with the coefficient to randomized group as the primary estimand. Missing outcome data will be imputed using multiple imputation based on predictions from the logistic regression model of the outcome. Sensitivity analyses will include analyses in which patients lost to follow-up are assumed to not have been hospitalized, and tipping-point analyses systematically and comprehensively varying assumptions about missing outcomes on the treatment and placebo arms independently.

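### Section 9.2 credits a power gain to a Kaplan-Meier analysis that is not the primary one, and 9.4.2 and 9.4.3, read literally, impute over an event documented before consent withdrawal

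*Combined protocol and SAP*

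**What the plan says.** **Primary analysis and power.** Section 9.2 bases power on a two-proportion Z test, "assuming a binary outcome with 5% non-informative loss to follow-up before 21 days", and gives 80% power with 95 complete observations per arm for 25% against 10%. It then adds: "The primary Kaplan-Meier analysis will yield slightly better power by treating the outcomes of patients lost to follow-up as censored" at last follow-up.

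Section 9.4.2 defines the primary analysis differently: a logistic regression on age, sex, race, ethnicity, risk group and arm, "with the coefficient to randomized group as the primary estimand". Log-rank and Cox analyses appear only in 9.4.9, among the exploratory analyses. Section 9.4.1 says: "Data subject to censoring (e.g., hospitalization) will be summarized by Kaplan-Meier estimate".

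**Incomplete follow-up.** Section 9.4.2: "Outcomes of subjects who withdraw consent or are otherwise lost to follow-up before 21 days will be considered missing". Then: "Missing outcome data will be imputed using multiple imputation based on predictions from the logistic regression model of the outcome". The sensitivity analyses include "analyses in which patients lost to follow-up are assumed to not have been hospitalized", plus a tipping-point analysis by arm. Section 9.4.3 applies the same missing-outcome rule to the secondary endpoints and follows the primary procedures.

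**Related definitions.** Sections 4.1 and 7.3 reserve loss to follow-up for patients whose hospitalization status or outcome cannot be established. Section 7.2 keeps following patients who withdraw to at least day 21, so far as that is allowed. Section 9.2 expects little loss because "the endpoint is designed to be evaluable by chart review unless the subject withdraws consent", which singles out consent withdrawal as the exception.

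**The concern.** There are two separate issues.

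1. Section 9.2 and section 9.4.2 give the same patients two incompatible treatments, censored in one and missing and imputed in the other, and name two different primary analyses. A power statement should describe the test that will be run.

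2. Censoring keeps an event seen before the patient leaves. The rule in 9.4.2, taken at its word, does not. A patient admitted on day 6 who withdraws consent on day 10 falls under the missing-outcome sentence, and the known admission is replaced by draws from the model. If patients withdrew because they were admitted, and did so unevenly by arm, the primary odds ratio would be biased by discarding data the trial already holds.

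**Working it through.** **Inputs.** From 9.2: 25% placebo and 10% resveratrol, two-sided 5%, 95 complete per arm, 5% non-informative loss. From the synopsis: 100 per arm. Assumed, because the documents do not say: event and loss times uniform over 21 days, and all loss taken as consent withdrawal. The second assumption makes the counts in step 2 an upper limit for that timing.

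**1. The plan's own power figure.** With pooled rate 0.175:

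- null SE = √(2 × 0.175 × 0.825 / 95) = 0.0551
- alternative SE = √((0.25 × 0.75 + 0.10 × 0.90) / 95) = 0.0540
- power = Φ((0.15 − 1.96 × 0.0551) / 0.0540) = Φ(0.776) = 78.1%

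Exact enumeration of the same test gives 79.2%. The approximation reaches 80% at 95 per arm with a resveratrol rate of 9.7%, so the stated 80% at 10% reproduces to rounding.

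**2. Known events discarded under the literal rule.** Expected count = patients × event rate × loss rate × probability that the event precedes the loss.

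- Placebo: 100 × 0.25 × 0.05 × 0.5 = 0.625
- Resveratrol: 100 × 0.10 × 0.05 × 0.5 = 0.25

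If all loss came at the very end of the 21 days, the last factor would be 1 and the counts 1.25 and 0.5. About 35 events are expected in all (25 + 10).

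**3. Effect on power and estimates.** Simulated arm-only logistic regression with multiple imputation, 5% non-informative loss:

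| Handling | Rates | Power |
|---|---|---|
| Literal rule | 25.0% / 10.0% | 78.1% |
| Known events kept, others imputed at full 21-day risk | 25.5% / 10.2% | 79.1% |
| Known events kept, others imputed at remaining risk | 25.0% / 10.0% | 79.4% |
| Kaplan-Meier day-21 difference | not tabulated | 80.9% |

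A second, smaller simulation gave 77.8% for the literal rule, 78.9% with known events kept and imputation at full risk, and 80.7% for Kaplan-Meier. The literal rule costs about one point and introduces no bias in this case.

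The slight overstatement in the second row follows by arithmetic: (23.75 + 0.625) / 95.625 = 25.5% and (9.5 + 0.25) / 95.25 = 10.2%. The odds ratio is (9.75/85.5) / (24.375/71.25) = 0.333, unchanged under equal loss.

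**4. Does the claimed gain carry over to 9.4.2?** The table omits the planned covariates. Adding them under the literal rule, with assumed prognostic strengths, gave:

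| Assumed odds ratios (per SD of age; risk group) | Power |
|---|---|
| No prognostic effect | 77.9% |
| 1.5; 1.8 | 78.5% |
| 1.8; 2.5 | 81.1% |
| 2.2; 3.3 | 82.8% |

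Part of the Kaplan-Meier advantage also exists with no loss at all (81.1% against 79.9% in one check, 81.7% against 80.4% in another), so it comes from the test statistic and not from censoring. The direction of the difference between Kaplan-Meier and 9.4.2 depends on covariate strength, which the documents do not give.

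**5. If withdrawal is related to the event (assumed range).** Discarding 10% or 20% of placebo events and none on resveratrol gives odds ratios of (10/90)/(22.5/75) = 0.37 and (10/90)/(20/75) = 0.42, against 0.33. The 20% end is five events, equal to the whole expected loss in that arm, so it is an extreme. Discarding equal proportions in both arms leaves 0.33. Discarding equal counts does not: two per arm gives (8/90)/(23/75) = 0.29.

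**The case against.** The best defence is that the Kaplan-Meier sentence is a leftover. The heading and estimand in 9.4.2 and the exploratory place of survival methods in 9.4.9 show which analysis governs, and the 80% figure comes from the two-proportion test and does not rely on that sentence. This stands. It limits the point to a text conflict and an unsupported remark. A reader might infer that the primary analysis is undetermined, or that the power remark has been shown false for 9.4.2. The documents support neither: 9.4.2 governs, and step 4 shows the comparison can go either way.

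On withdrawal, the defence is that 4.1 and 7.3 confine loss to undetermined outcomes, 7.2 continues follow-up where allowed, and the endpoint rests on record review, so the intent is probably to set to missing only what was not ascertained. That is a fair reading of intent. But 9.4.2 names consent withdrawal in its own right, and the 4.1 and 7.3 definitions do not clearly reach it.

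A reader might also infer that the not-hospitalized sensitivity analysis would recode a known admission as no event. That requires withdrawal to count as loss while escaping the definitions of loss as undetermined status. If it counts as loss, those definitions protect the known event; if it does not, that sensitivity analysis does not apply to it. Nor does 9.4.1 conflict with 9.4.2, since it only concerns how data are summarized.

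Finally, the tipping-point analysis would show whether the result depends on these patients. It would do so only as a sensitivity analysis, with the primary estimate still leaving out known events.

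**Conclusion.** The point holds in two limited parts. Section 9.2 attaches a power gain to an analysis that is not primary, and the gain is unsupported for 9.4.2. The missing-outcome rule in 9.4.2 and 9.4.3 has no exception for an event documented before consent withdrawal.

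Under the plan's own 5% non-informative loss the second part is small: up to about 0.6 placebo and 0.25 resveratrol events with uniform timing, no bias, and about one point of power in an arm-only model. Material bias needs withdrawal to depend on the event and to fall unevenly by arm. The documents give no rate for that, so the odds ratios of 0.37 to 0.42 illustrate an assumption and are not a forecast. The trial's power claim is not overturned: 78.1% (79.2% exact) against a stated 80% is a rounding. The plan should still be corrected, because a stated rule can discard a known event and the correction is nearly free.

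**What to change.** 1. **Section 9.2.** Delete the Kaplan-Meier sentence. Name the logistic regression in 9.4.2 as the single primary analysis. Describe the two-proportion calculation as a fixed-design approximation to it, with about 78% power (78.1% by normal approximation, 79.2% exact) at 95 per arm for 25% against 10%. The fixed-design label matters because 9.4.6 sets group-sequential bounds that this figure does not include.

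2. **Sections 9.4.2 and 9.4.3.** State that an endpoint event documented on or before withdrawal or last contact, or ascertained later as allowed under 7.2, counts as an event. State that only outcomes still undetermined at day 21 are missing, and that imputation, the not-hospitalized analysis and the tipping-point analysis apply to those outcomes alone.

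Conditioning the imputation on event-free time already observed is optional. Imputing at full 21-day risk gives 25.5% and 10.2% and leaves the odds ratio unchanged when loss is equal between arms.

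**Cost.** Wording in three sections. No added patients, visits or data: admission dates come from the hospital records already requested, and last-contact dates from the surveys and calls already planned.
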